#### 4.2.3. Secondary outcomes

1. Summarize continuous measures of VRC01LS and 10-1074 trough concentrations in serum at Step 1, Week 4 and Week 8, and monthly during Step 2 through 24 weeks of

follow-up. Median values overall will be reported, and stratified by successes and failures in Step 2.

2. Proportion of children with trough VRC01LS and 10-1074 concentrations below defined trough values at Step 1 Week 4 and Week 8, and monthly during Step 2 through 24 weeks of follow-up (including exact confidence limits).
3. Monthly height measurements will be standardized using WHO Z-scores (for age and sex) and described at each scheduled measurement time from Step 1, Day 0 through Week 24 of Step 3. Mean changes (with 95% confidence intervals) will be obtained from Step 1, Day 0 to Step 2, Day 0 (representing change during the period of dual bNAbs + ART), from Step 2, Day 0 to Step 3, Day 0 (representing change during the period of dual bNAbs without ART), and from Step 1, Day 0 to Step 3, Week 24 (the period of complete follow-up).
4. The previous analysis will be repeated for monthly Z-score weight measurements.
5. Summarize anti-drug antibody (ADA) results for each bNAb; if warranted based on initial assessment, summarize by successes and failures in Step 2.

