1.9. Primary Endpoints and Analyses

Aim 1: The primary endpoints will be (1) the frequency and severity of treatment-associated adverse events, and (2) the proportion of children who maintain HIV-1 plasma RNA <400 copies/mL (and <40 copies/mL), after initiating VRC01LS and 10-1074 infusions (24 weeks after withdrawal of standard ART). Secondary endpoints will include pharmacokinetic profiles of all children who receive VRC01LS and 10-1074 and growth characteristics (height and weight z-scores) of virally suppressed children receiving bNAbs.

Aim 2: Viral reservoirs during treatment with VRC01LS and 10-1074 will be evaluated in blood samples (PBMCs) using a novel single-template, near full-length viral sequencing assay that provides information on the complete spectrum of HIV-1 DNA copies integrated into host chromosomes. This approach will allow us to evaluate defective vs. intact HIV-1 genomes, antiretroviral drug and cytotoxic T-lymphocyte (CTL) escape variants and longitudinal viral sequence evolution in total CD4 T cells as well as in phenotypically-complex subsets of CD4 T cells known to be critical for viral reservoir stabilization. Cell-associated HIV-1 RNA and plasma RNA will be simultaneously analyzed and sequenced. If rebound occurs during analytic treatment interruption (ATI), viral reservoir parameters will be correlated to viral rebound kinetics, to pharmacokinetic measurements of bNAbs, and to antiviral immune parameters determined in Specific Aim 3.

Aim 3: We will use comprehensive phenotypic and functional assays to profile effects of VRC01LS and 10-1074 treatment on biomarkers of immune activation and on innate cellular immune responses, coupled with RNA-Seq-based gene expression studies in selected immune cell subsets. In addition, the evolution of neutralizing antibody breadth and the frequency and functionality of HIV-1-specific T cells will be analyzed, and combined with viral sequencing data (generated in specific aim 2) to identify viral immune escape.

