3. PRIMARY OBJECTIVES

Specific Aim 1: To conduct an interventional clinical trial to determine the safety, pharmacokinetics, dosing and antiviral efficacy of up to 24 weeks of maintenance VRC01LS and 10-1074 immunotherapy in early-treated HIV-1 infected children in Botswana. This uncontrolled, open-label clinical trial will be conducted at two sites in Botswana, using established clinical research infrastructure provided by the Botswana-Harvard Partnership (BHP). The primary endpoints of this study will be the frequency and severity of treatment-associated serious adverse events, and the proportion of children who maintain HIV-1 plasma RNA <400 copies/mL (and <40 copies/mL) 32 weeks after initiating dual bNAb treatment (24 weeks after withdrawal of standard ART). Secondary endpoints will include pharmacokinetic profiles of all children who receive VRC01LS and 10-1074 and growth characteristics of virally suppressed children receiving bNAbs.

Specific Aim 2: To evaluate effects of treatment with VRC01LS and 10-1074 on the size and cellular composition of residual viral reservoirs. Viral reservoirs during treatment with bNAbs will be evaluated in blood samples using a novel single-template, near full-length viral sequencing assay

that provides information on the complete spectrum of HIV-1 DNA copies integrated into host chromosomes. This approach will allow for evaluation of defective vs. intact HIV-1 genomes, antiretroviral drug and CTL escape variants and longitudinal viral sequence evolution in total CD4 T cells as well as in phenotypically-complex subsets of CD4 T cells known to be critical for viral reservoir stabilization. Cell-associated HIV-1 RNA and plasma RNA will be simultaneously analyzed and sequenced. Viral reservoir parameters will be correlated to viral rebound kinetics during ATI, to pharmacokinetic measurements of VRC01LS and 10-1074, and to antiviral immune parameters determined in Specific Aim 3.

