Although this proof-of-concept Phase I/II study will not have a control group, an observed proportion of at least 30% suppression on dual bNAb therapy would provide reasonable evidence of a positive effect of VRC01LS + 10-1074 in maintaining virologic suppression, as maintenance of HIV-1 RNA <400 copies/mL is unlikely in the absence ART, even for early-treated children. As noted above, data from children treated in the first year of life in CHER [52] and in Kenya [58] showed that few children remain suppressed to a threshold of <400 copies/mL at 6 months off ART. In CHER, only 2 of 183 children were suppressed to <400 copies/mL at 6 months (one of whom has remained suppressed for > 9 years, and the other rebounded at ~ 8 months). Additional data from Aims 2 and 3 that correlate viral reservoir (pre-ART, and pre- and post-bNabs) and maintenance of viral suppression, and

associations between immune responses and viral control, will bolster interpretation of the specific effect of VRC01LS + 10-1074 on maintenance of viral suppression.

10.1.3. Dynamics of viral decay and rebound: Based on frequent HIV RNA monitoring after ART withdrawal, the kinetics of viral rebound (if rebound occurs) will be summarized descriptively. Analyses will assess viral suppression off-ART (yes vs. no) and time to HIV RNA ≥ 400 (and ≥ 40) copies/mL, and will evaluate associations of these metrics with pre-ART and on-ART virologic and immunologic measures including immune activation and anti-HIV immune responses (binary regression; rank correlations analyzing infants with sustained undetectable HIV RNA off-ART as the lowest rank).

10.1.4. Growth assessments: Child weight and height will be measured at least every month, and WHO standardized Z-scores will be evaluated for changes over time (beginning with pre-intervention data from the EIT study), and compared with data from prior studies for children on continuous ART. Although neurodevelopmental assessments would be of interest, the small number of children in this cohort and lack of an appropriate comparator group would preclude meaningful information from being obtained from standard neurodevelopmental testing.

10.2. Data Analysis and Statistical Considerations for Specific Aim 2

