## **3.2 Specific Aim 1 Secondary Outcome Measures**

- VRC01LS and 10-1074 concentrations in serum measured through week 32 following Step 1 entry
- Growth characteristics (sex-specific WHO standardized Z-scores for height for age and weight for age) measured at least monthly, including growth trajectories.

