#### 4.1.3 Visit windows and schedule

The baseline visit, as defined above, is considered day 0. Baseline measurements are the last available measurement for a given parameter obtained prior to administration of this first infusion. The visit schedule is based on this day 0.

Per protocol, the scheduled visit window begins at the midpoint from the previous visit and extends to the midpoint with the next visit. During participation in Step 1 or Step 2, if a child needed to discontinue study treatment for any reason, he/she would complete final visit evaluations for the Step and enroll to Step 3.

Children enrolled to **Step 1a** (first 6 participants) had initial visits at Day 0, Day 1, Week 1, Week 4, Week 4 + 1 day, Week 5 and Week 8. Infusions occurred at Day 0, Week 4 and Week 8. Single PK draws were made at all non-infusion visits and at Week 8, while more intensive PK draws occurred on Day 0 (pre-infusion, end of infusion and 1 hour post-infusion) and Week 4 (pre-infusion, end of infusion and 1 hour post infusion at Week 4). The Step 1a follow-up extended beyond Week 8 at 2 week intervals until Week 32 (which also served as Step 2 Week 0), with infusion and single PK draws every 4 weeks. SMC review and approval of Step 1a results was required prior to starting Step 2

**Step 1b** (for participants enrolled after the first six participants in Step 1/SMC review) visits were scheduled at Day 0, Week 1, Week 4, Week 5 and Week 8 (Step 2 Week 0). Dual bNAbs were administered at Day 0, Week 4 and Week 8; PK measures were limited to pre-dose trough at Week 4 and Week 8 (which also served as Step 2 Week 0).

If a participant had a confirmed viral load result  $\geq 40$  copies/mL during Step 1 (either 1a or 1b), he/she would discontinue bNAbs, complete visit procedures equivalent to those outlined for Step 1 Week 8, and enter Step 3 (and not participate in Step 2).

**Step 2** visits occurred every week for the first 4 weeks, then every 2 weeks through Step 2, Week 24, with dual bNAbs administered and PK trough draws every 4 weeks.

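### The SAP growth analysis leaves out the pre-intervention EIT Z-scores and the continuous-ART comparison in protocol 10.1.4, and averages Z-score change over phases of unequal length

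*SAP*

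**What the plan says.** Protocol 10.1.4 sets two references for growth. The series starts before treatment: "WHO standardized Z-scores will be evaluated for changes over time (beginning with pre-intervention data from the EIT study"). It is then to be "compared with data from prior studies for children on continuous ART".

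The protocol states the secondary endpoint as "growth characteristics (height and weight z-scores) of virally suppressed children receiving bNAbs" (section 1.9), and in nearly the same words as "growth characteristics of virally suppressed children receiving bNAbs" (section 3).

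SAP 3.2 lists height and weight Z-scores "measured at least monthly, including growth trajectories", with no trajectory method. SAP 4.2.3, items 3 and 4, describes Z-scores at each scheduled visit from Step 1 Day 0 to Step 3 Week 24. It then gives mean changes with 95% confidence intervals for three spans: Step 1 ("from Step 1, Day 0 to Step 2, Day 0 (representing change during the period of dual bNAbs + ART")), Step 2 Day 0 to Step 3 Day 0, and Step 1 Day 0 to Step 3 Week 24. The analysis population is every child with any Step 1 infusion (SAP 4.1.2).

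On phase length, SAP 4.1.3 says "The Step 1a follow-up extended beyond Week 8 at 2 week intervals until Week 32", whereas children enrolled later spend 8 weeks in Step 1. A child with confirmed HIV RNA of 40 copies/mL or more in Step 1 is to stop bNAbs "and enter Step 3 (and not participate in Step 2").

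**The concern.** The trial is uncontrolled. The EIT series is the protocol's within-child reference on ART before any bNAb, and the prior-study comparison is its external one. An analyst who follows the SAP produces neither. Reduced growth toxicity is part of the protocol's case for time off ART (sections 2.1.1 and 13.4.2.1), so the reference matters for interpretation.

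The omission is not explained elsewhere. Growth belongs to Specific Aim 1, which this SAP covers (SAP 2.2), so the statement that other objectives are handled separately does not apply. The SAP version history records no decision to drop either element. The EIT variables in SAP 4.2.1 include birth weight but no height or weight series.

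Separately, a change score depends on elapsed time, and each phase mean pools children observed for different times. SAP 4.3 recognises the 32-week versus 8-week split for trough levels and as a possible rebound risk factor, but 4.2.3 does not use it for growth.

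**Working it through.** **The plan's own figure.** Protocol 7.8 gives a minimum follow-up of 56 weeks. Step 1 + Step 2 + Step 3 = 8 + 24 + 24 = 56, which reproduces it. With a 32-week Step 1a the sum is 32 + 24 + 24 = 80.

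**Inputs.** Six Step 1a children at 32 weeks, the others at 8 (SAP 4.1.3, 4.3); N from 20 to 36 (protocol 5.5); success rates of 70% and 30% (protocol 2.3.1, 10.1.2); Step 3 Day 0 is the day of ART restart (protocol 7.7.1).

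**Step 1 interval**, assuming all children complete Step 1.
- N=20: mean length (6×32 + 14×8)/20 = 304/20 = 15.2 weeks. Step 1a is 6/20 = 30% of children and 192/304 = 63% of child-weeks.
- N=36: (6×32 + 30×8)/36 = 432/36 = 12.0 weeks. Step 1a is 6/36 = 17% of children and 192/432 = 44% of child-weeks.

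**Step 2 interval at N=20.** Assume that all rebounders restart ART at one common week w, from 1 to 22.
- 70% success, 6 rebounders: (14×24 + 6w)/20 = 17.1 weeks at w=1 and 23.4 at w=22.
- 30% success, 14 rebounders: (6×24 + 14w)/20 = 7.9 weeks at w=1 and 22.6 at w=22.

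**Full follow-up.** Without rebound it is 80 weeks (Step 1a) or 56 (Step 1b). With ART restart at Step 2 week w it is 32 + w + 24 = 56 + w, or 8 + w + 24 = 32 + w. At w=1 these are 57 and 33 weeks. One mean therefore spans 33 to 80 weeks among children who enter Step 2. Children who go from Step 1 to Step 3 have no Step 2 Day 0 and so drop out of both phase means; the SAP does not say this.

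**Possible numerical shift.** The documents give no Z-score drift and no SD of change. For an assumed constant drift d of 0 to 0.5 Z per year, the pooled Step 1 mean exceeds a common 8-week mean by (mean length − 8)×d/52:
- N=20: (15.2 − 8)×0.5/52 = 0.069 Z, so 0 to 0.069.
- N=36: (12.0 − 8)×0.5/52 = 0.038 Z, so 0 to 0.038.

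**Precision, in units of the SD of change.** The 95% half-width is t(0.975, n−1)/√n: 1.05 for n=6, 0.58 for n=14, 0.47 for n=20.

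**The case against.** **The means are descriptive and no phases are contrasted.** This stands. Each mean can be read against zero. Z-scores already remove normal growth for age and sex, and visit-level values let a reader see fixed time points. But the SAP attaches treatment labels and confidence intervals to the phase means, and a reader will look at their size. Visit-level description also supplies neither missing reference.

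**Detail may sit in the Analysis Implementation Plan.** SAP 1.1 assigns table, figure and coding outlines to that plan, which is not among the documents. It may settle layout. A comparison named in the protocol still belongs in the SAP.

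**Step 3 already provides ART alone in the same children.** It does, for 24 weeks. It follows the intervention, and for some children follows rebound, so it adds to a pre-intervention reference without replacing it.

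**A reader might infer that the SAP contradicts the protocol by including rebounders.** The documents do not support that. The protocol's wording about suppressed children can mean children who stay suppressed, but protocol 1.5 and SAP 2.1 describe the enrolled population in the same terms. Under that reading there is no conflict. A rebounder's Step 2 interval also ends at ART restart. RNA is tested weekly and then every two weeks, results are due in under 7 days (protocol 7.4), and restart is intended within days (7.2). Most of that interval should precede rebound, so the main effect is a shorter interval. Restricting the main summary to children suppressed through Week 24 would select on a post-baseline outcome.

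**Subgroup splits are costly.** This stands. At 70% success the six Step 1a children split into about 4 and 2 by rebound status, with half-widths of 1.59 and 8.98 SD. A slope is preferable to a four-way split.

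**Conclusion.** The concern holds in two parts. First, the SAP omits two elements that protocol 10.1.4 specifies for growth and gives no reason; this rests on the text alone. Second, the phase means pool intervals that differ fourfold in Step 1 (32 versus 8 weeks) and vary with time to ART restart in Step 2, so the sizes of the labelled changes refer to no defined period.

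The consequence is modest. Growth is a secondary, descriptive outcome, and the sample size, primary endpoints and stopping rules are unaffected. The shift of 0 to 0.069 Z at N=20 rests wholly on the assumed drift. Whether it would be visible within the confidence interval cannot be judged without an SD. Inclusion of rebounders is an ambiguity to clarify and should not be reported as an error.

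**What to change.** Revise SAP 4.2.3, items 3 and 4:

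1. Report the Step 1 change from Day 0 to Week 8 for all children with a Week 8 measurement. Show the 32-week Step 1a change separately and descriptively.
2. Keep the Step 2 change for all children who enter Step 2 as the main summary, with n and interval lengths. Add children suppressed through Week 24 and rebounders as a supplementary description, and note that this groups children by a post-baseline outcome. State which children the protocol's endpoint wording means.
3. Report full follow-up as a per-week slope from actual visit dates. List the children who leave Step 1 for Step 3.
4. Add the available EIT height and weight Z-scores before the first bNAb dose, in a stated window, as the within-child on-ART reference. For children from the PK Step this reference ends more than 20 weeks before Step 1 if they are among the first six (first to third dose 8 weeks, then more than 12), so the gap should be shown.
5. Restore the comparison with prior continuous-ART studies and name its source, or state why it was dropped.

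Cost: SAP wording, analysis time and record linkage, with no new visits. Protocol 7.11 and 5.6 make EIT records available and shareable, but that height and weight were recorded at each EIT contact is an assumption. Some Week 8 measurements may be missing, since the COVID-19 letter of amendment allowed remote visits for the first six children. Intervals for those six will be wide, at about 1.05 SD either side.

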#### 4.3. Exploratory objectives

1. Compare trough VRC01LS and 10-1074 levels at Step 2 entry between children who ultimately remained suppressed (<400 through Step 2) versus those who rebound to  $\geq 400$  during Step 2 (restricting to children who start Step 2). Sub-analysis of levels for children who were in Step 1a (first six children) will be performed (as these six children received bNAbs in addition to ART for 32 weeks whereas subsequent children received bNAbs in addition to ART for 8 weeks).
2. Compare trough levels at end of Step 2 for children suppressed (<400 through Step 2) to levels at time of rebound to  $\geq 400$  for children who rebound during Step 2 (restricting to children who start Step 2).
3. Correlate trough levels at Step 2 entry with time of rebound  $\geq 400$  with censoring at 32 weeks (restricting to children who start Step 2).
4. Correlate trough levels at end of Step 2 for children suppressed (<400 through Step 2) and trough levels at time of rebound to  $\geq 400$  for children who rebound during Step 2 with time to rebound (censoring at 32 weeks).
5. Evaluation of potential risk factors for viral rebound to  $\geq 400$  copies/mL at/before 24 weeks in Step 2 (yes/no) (restricting to children who start Step 2). Risk factors may include demographic variables, HLA type, baseline plasma HIV RNA and PBMC DNA prior to ART (from the EIT study), PMBC DNA at Step 1 and Step 2 entry, history of prior virologic rebound on ART, duration of dual bNAb treatment (extended >8 weeks for participants in

Step 1a versus 8 weeks for other participants), trough PK values for each bNAb during Step 2 (time dependent variable), and presence of pre-defined HIV envelope sequences associated with resistance to either bNAb (earliest available in life, closest available prior to rebound, and at rebound). The extent of risk factors considered will be dependent on availability of results for these factors at the time of analysis. Analyses will compare characteristics of participants who experience rebound versus those who do not experience rebound using Fisher's Exact Test for categorical variables and Wilcoxon's Test for continuous variables).

